8.2.1. Inclusion Criteria

Inclusion criteria are specified by each study aim. Within each aim, patients must meet all of the following criteria to be eligible for inclusion in the study:

8.2.1.1. Aim 1 Inclusion Criteria

- Born in 2005 or earlier (as age 18 or older in 2023, owing to the data providing year but not month or day of birth).
- At least one year of pharmacy and medical enrollment in HealthVerity prior to index date (FDA EUA date per vaccine). A gap of up to 30 days will be allowed.
- Have been a State of California/Louisiana resident for at least one year prior to index date (FDA EUA date per vaccine)

8.2.1.2. Aim 2 Inclusion Criteria

- Born in 2006 or later (as age 0-17 years in 2023, owing to the data providing year but not month or day of birth)
- 2) At least six months of pharmacy and medical enrollment in HealthVerity prior to index date (FDA EUA date per age group vaccine). Six months was selected to allow for analysis to include children age <1 year. A gap of up to 30 days will be allowed.

- Have been a State of California/Louisiana resident for at least six months prior to index date (FDA EUA date per age group and vaccine)

8.2.1.3. Aim 3A Inclusion Criteria

Aim 3A criteria are different based on the pediatric and adult population analyses as follows:

8.2.1.3.1. Aim 3A Adult Inclusion Criteria

- Born in 2005 or earlier (as age 18 or older in 2023, owing to the data providing year but not month or day of birth).
- Hospitalized for COVID-19 (an inpatient encounter with ICD-10-CM U07.1 "COVID-19" in the principal diagnosis position)
- At least one year of continuous pharmacy and medical enrollment in HealthVerity prior to index date (i.e. hospitalization date). A gap of up to 30 days will be allowed.
- Have been a State of California/Louisiana resident for at least one year prior to index date (i.e. hospitalization date)

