8.4.2. Health Verity's Administrative Claims Data

HealthVerity closed claims will be limited to approximately 19 million patients residing in California and approximately 3.8 million in Louisiana. Patients who were California/Louisiana residents in the HealthVerity claims database will be defined using the following hierarchical definition:

- Persons who have their most recent enrollment file record indicating a patient location of California or Louisiana in HealthVerity claims enrollment file.
- 2. Persons who have a patient state location other than California/ Louisiana in HealthVerity claims enrollment but have one or more records in the California/ Louisiana Immunization Registry. Examples include people who previously lived in Texas but moved to California and received a vaccine, or persons who crossed state lines for a vaccine and remain in their non-California state in claims data.

HealthVerity's description of their data is that they are generally representative of the age and sex distribution of the population. For our specific research context, samples created from HealthVerity claims also generally follow California's demographic patterns with respect to age & sex. However, there are several caveats to note. Our claims population is slightly more female and young people (particularly age 5-17) are overrepresented in our claims relative to other groups. Children under 5, and adults 65+, are slightly underrepresented.

The California subset of HealthVerity does not include patients in the Kaiser Permanente network. Insurers contributing to closed claims in both states include a mix of commercial payers, Medicare Advantage/Part C pains, and Medicaid Managed Care plans. Data elements include patient demographic information, inpatient/outpatient visit-level information such as diagnoses, procedures, and length of stay, hospital characteristics, and medication information. Owing to the nature of claims, the data represent the final set of diagnoses over the course of the hospitalization sent to the patient's insurer for reimbursement, with diagnosis prioritization assigned by clinicians or hospital staff. For inpatient encounters, the data will be assumed to represent the overarching events during hospitalization and may be less subject to rule out diagnosis codes than electronic health record data.

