- An inpatient encounter with ICD-10-CM U07.1 "COVID-19" listed in any diagnosis position. As a sensitivity analysis, we will restrict to U07.1 in primary diagnosis field.
- An emergency department encounter with ICD-10-CM U07.1 "COVID-19" code
- COVID-19 critical illness, defined as intensive care unit [ICU] admission, mechanical ventilation, or inpatient death. If sample size allows, we will evaluate VE against each component separately in order to support V&E models.

PFIZER CONFIDENTIAL

CT24-WI-GL02-RF02 5.0 Non-Interventional Study Protocol Template For Secondary Data Collection Study 01-Aug-2023

Negative control outcomes such as accidental injury, ingrown toenail or atopic dermatitis

Exploratory outcomes:

- An urgent care encounter with ICD-10-CM U07.1 "COVID-19" code
- All-cause mortality within 3-months of COVID-19 encounter, regardless of setting
- All-cause mortality within 3-months of COVID-19 outpatient encounter
- All-cause mortality within 3-months of COVID-19 inpatient encounter
- All-cause mortality within 3-months of COVID-19 emergency department encounter
- All-cause mortality within 3-months of COVID-19 critical illness
- 7. All-cause mortality within 3-months of COVID-19 urgent care encounter

Measures of absolute and relative VE: For each outcome above, results will be calculated as:

- 1. Absolute VE comparing vaccinated to unvaccinated persons, regardless of prior vaccination
- Relative VE will be calculated for each of the following mutually exclusive subgroups.
 - xBB.1.5 vaccinated vs xBB.1.5 unvaccinated persons who received BA.4/5 bivalent vaccine.
 - b. XBB.1.5 vaccinated vs XBB.1.5 unvaccinated persons who did not receive BA.4/5 bivalent vaccine but did receive at least 2 doses of mRNA vaccine (regardless of formulation).
 - xBB.1.5 vaccinated vs never COVID-19 vaccinated.

Stratifications: Results will be stratified by age group (overall, age 18-49, 50-64, 65+) as well as by calendar time (BA.4/5 versus XBB.1.5 vaccine available eras).

[figure not shown]

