5.3.2. Outcomes

The outcomes of interest are presented in Table 5.2.

Table 5.2 Outcomes Variables

Outcome Type	Variable	Data source(s)	Operational definition	
Primary outcome	COVID-19 diagnosis	HV Claims	Any encounter regardless of diagnosis setting with ICD-10-CM code: U07.1.	
Secondary outcomes	COVID-19 outpatient encounter	HV Claims	Outpatient encounter with ICD-10-CM code: U07.1	
	COVID-19 hospitalization	HV Claims	Hospitalizations "for COVID-19" were defined as those with an inpatient encounter at an acute care facility with ICD-10-CM code: U07.1 "COVID-19" that did not have an additional incidental code (for unintentional injury, physical trauma, poisoning, short-stay (<2 days) childbirth or severe and persistent mental illness) or a U07.1 hospitalization where treatment used solely for COVID-19 (eg, remdesivir) was identified regardless of accompanying diagnoses.	
			As a sensitivity analysis, we will relax this definition to consider any hospitalization with a U07.1 code, without consideration of incidental findings.	
	COVID-19 emergency department visit	HV Claims	Emergency department visit with ICD-10- CM code: U07.1	
	COVID-19 critical illness	HV Claims	Intensive care unit [ICU] admission, mechanical ventilation, or inpatient death. If sample size allows (Section 5.5), we will evaluate VE against each component separately	

Outcome Type	Variable	Data source(s)	Operational definition
	Non-COVID- 19 respiratory infections (pneumonia, respiratory syncytial virus (RSV), rhinovirus, antibiotic prescriptions)	HV Claims	Any encounter regardless of setting with ICD-10-CM code for diagnosis or NDC codes for antibiotics (codes in the Protocol Annex). If sample size allows (Section 5.5), we will evaluate VE against each component separately
	Negative control outcome, such as accidental injury, ingrown toenail or atopic dermatitis	HV Claims	Any encounter regardless of setting, with ICD-10-CM code for negative control outcomes (codes in the Protocol Annex)
Exploratory outcomes	COVID-19 urgent care encounter	HV Claims	An urgent care encounter with ICD-10-CM code: U07.1 "COVID-19"
	All-cause mortality after COVID-19 encounter	HV Claims and HV Mortality Database	HealthVerity ID in Mortality Database within 3-months of COVID-19 encounter, regardless of setting
	All-cause mortality after COVID-19 outpatient encounter	HV Claims and HV Mortality Database	HealthVerity ID in Mortality Database within 3-months of COVID-19 outpatient encounter

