5.2.1.2. Aim 3B Pediatric Inclusion Criteria

- 1. Born in 2005 or later (as age 0-17 years in 2023, owing to the data providing year but not month or day of birth)
- 2. Has COVID-19 diagnosis (ICD-10-CM code U07.1) in any setting, any position between 01 June 2022 and 30 November 2022 (first eligible code is the index date).
- 3. At least six months of pharmacy and medical enrollment in HealthVerity prior to index date. Six months was selected to allow for analysis to include children <1 year due to patient privacy measures in HealthVerity data. A gap of up to 30 days will be allowed
 - So, for the pediatric patients, the minimum age will be 6 months due to this requirement of six months of baseline period.
- 4. Have been a State of California/Louisiana resident for at least six months prior to index date
- 5. Have continuous medical and prescription insurance coverage for at least 30 days after the index date (follow-up period).
 - The duration of the follow-up period will be required to be at least 1 month.

NOTE: since the evaluation of the long-term HCRU and cost starts from 1 month after the index date, this requirement for patients to have at least one month of follow-up is needed for this study.

The index COVID-19 hospitalizations will be identified between 01 June 2022 and 30 November 2022 (COVID identification period)

- To avoid the incidental identification of COVID-19, hospitalizations for COVID-19 were defined as those with an inpatient encounter at an acute care facility with ICD-10-CM code U07.1. Furthermore, hospitalizations did not have an additional incidental code (for unintentional injury, physical trauma, poisoning, short-stay [<2 days] childbirth or serious psychiatric admissions), or a U07.1 hospitalization where treatment used solely for COVID-19 (eg, remdesivir) was identified regardless of accompanying diagnoses.
- The earliest claim will be identified as the index event with the corresponding date (hospital admission date) as the index date.

Patients who were California or Louisiana residents in the HealthVerity claims database will be identified using the following hierarchical definition:

- 1. Have a location of California or Louisiana indicated within their HealthVerity claims enrollment file record.

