3. RATIONALE AND BACKGROUND

Until recently, vaccine registries were not available for de-identification and linkage to secondary claims-based databases. However, through a collaboration with HealthVerity, a leading supplier of secondary health data, the State of California and the State of Louisiana have made their vaccine registries available for linkage for research purposes. California and Louisiana deidentify the registries, using HealthVerity's software to convert each patient's protected health information to a unique HealthVerity ID which can then be linked to the full HealthVerity database to gather clinical history and outcomes.

The purpose of this document is to detail the statistical methods and analyses that will be used in the HealthVerity claims database linked to the State of California/Louisiana's vaccine registries to address Aim 1 of the study protocol. Separate SAPs will be produced to address the other aims of the protocol.

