5.3.2. Outcomes

The outcomes of interest are presented in Table 5.2.

Table 5.2 Outcomes Variables

Outcome Type	Variable	Data source(s)	Operational definition
Primary outcome	COVID-19 diagnosis	HV Claims	Any encounter regardless of diagnosis position or setting with ICD-10-CM code: U07.1.
Secondary outcomes	COVID-19 outpatient encounter	HV Claims	Outpatient encounter with ICD-10-CM code: U07.1
	COVID-19 hospitalization	HV Claims	Hospitalizations "for COVID-19" were defined as those with an inpatient encounter at an acute care facility with ICD-10-CM code U07.1 "COVID-19" that did not have an additional incidental code (for unintentional injury, physical trauma, poisoning, short-stay [<2 days] childbirth or serious psychiatric admissions), or a U07.1 hospitalization where treatment used solely for COVID-19 (eg, remdesivir) was identified regardless of accompanying diagnoses. As a sensitivity analysis, we will restrict this definition to be more conservative by requiring the incidental finding code be the most frequently claimed during the inpatient encounter, as a proxy for primary diagnosis as HealthVerity does not provide this information. As a sensitivity analysis, we will relax this definition to consider any hospitalization with a U07.1 code, without consideration of incidental findings.
	COVID-19 emergency department visit	HV Claims	Emergency department visit with ICD-10-CM code: U07.1

Outcome Type	Variable	Data source(s)	Operational definition
	COVID-19 critical illness	HV Claims	Intensive care unit [ICU] admission, mechanical ventilation, or inpatient death. If sample size allows (Section 5.5), we will evaluate VE against each component separately
	Negative control outcome, such as accidental injury, ingrown toenail or atopic dermatitis	HV Claims	Any encounter regardless of setting, with ICD-10-CM code for negative control outcomes (codes in in the Protocol Annex)
Exploratory outcomes	COVID-19 urgent care encounter	HV Claims	An urgent care encounter with ICD-10-CM code: U07.1 "COVID-19"
	All-cause mortality after COVID-19 encounter	HV Claims and HV Mortality Database	HealthVerity ID in Mortality Database within 3-months of COVID-19 encounter, regardless of setting
	All-cause mortality after COVID-19 outpatient encounter	HV Claims and HV Mortality Database	HealthVerity ID in Mortality Database within 3-months of COVID-19 outpatient encounter

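### Aim 3A selects its cohort on a principal-diagnosis position that the Aim 1 SAP says the claims source does not provide

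*Protocol*

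**What the plan says.** Protocol sections 8.2.1.3.1 (adult) and 8.2.1.3.2 (pediatric) make a COVID-19 hospitalization the entry event for Aim 3A and require U07.1 "in the principal diagnosis position". The admission date is the index date. Section 8.7.3 follows patients from admission to discharge and compares cost, length of stay, ICU admission and other inpatient outcomes. Section 7 names inpatient expenditure, vaccinated against unvaccinated, as the main measure.

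For Aims 1, 2, 4 and 5 the protocol counts an inpatient encounter with U07.1 in any position and adds: "As a sensitivity analysis, we will restrict to U07.1 in primary diagnosis field" (sections 8.7.1, 8.7.2, 8.7.5 and 8.7.6).

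Table 5.2 of the Aim 1 SAP (16 January 2024) uses a different main definition: a U07.1 inpatient stay without an incidental code, or one with treatment used only for COVID-19. One of its two sensitivity analyses rests on the most frequently claimed code, "as a proxy for primary diagnosis as HealthVerity does not provide this information".

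On the data themselves, protocol section 8.4.2 says that claims hold the final set of diagnoses, "with diagnosis prioritization assigned by clinicians or hospital staff". The Aim 1 SAP repeats this in its own section 5.4.2.

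**The concern.** The principal-position rule is the only Aim 3A criterion that identifies a hospitalization for COVID-19. The index date, the enrollment and residency look-back, the vaccination status at admission and every outcome hang on it. If the field is not delivered, a programmer has to choose a substitute, and the protocol does not name one.

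The obvious candidate is protocol Table 4, which accepts U07.1 in any position. That would bring in stays where the infection was incidental to an injury, a poisoning or a psychiatric admission. Cost, length of stay and ICU use in such stays may not be due to COVID-19. Who is in the cohort, and so what the vaccinated and unvaccinated groups are being compared on, would then rest on a choice made at programming and not on a stated rule.

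**Working it through.** No formula applies, and the plan gives no figure to reproduce: section 8.5 declares sample size calculations not applicable, and there is no Aim 3A count. The check sets the texts side by side.

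**1. Same data source.** Protocol sections 8.4 and 8.4.2 describe one HealthVerity closed-claims source for all aims. The Aim 1 SAP uses that source (section 5.4). Its remark about primary diagnosis concerns the supplier's data, not something peculiar to Aim 1.

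**2. Hospitalization rules in each place.**

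| Place | Rule for a COVID-19 hospitalization |
|---|---|
| Protocol 8.2.1.3.1 and 8.2.1.3.2 (Aim 3A) | U07.1 in principal position; no alternative given |
| Protocol Table 4 | U07.1 in any position, acute care inpatient stay |
| Protocol 8.7.1, 8.7.2, 8.7.5, 8.7.6 (Aims 1, 2, 4, 5) | Any position; primary field as a sensitivity analysis |
| Aim 1 SAP Table 5.2 | No incidental code, or COVID-19-only treatment; two sensitivity analyses: incidental code must be the most frequently claimed, and any U07.1 stay |
| Aim 2 SAP Table 5.2 | Same approach; one sensitivity analysis: "we will relax this definition to consider any hospitalization with a U07.1 code, without consideration of incidental findings" |
| Aim 3B SAP 5.2.1.2 (index hospitalizations) | "hospitalizations did not have an additional incidental code", or COVID-19-only treatment |
| Aim 3B SAP Table 2 (follow-up hospitalizations) | COVID-19 discharge diagnosis in any position |

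No SAP among the documents uses diagnosis position to select stays.

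**3. Does any text say that a position field is delivered?** The sentence on diagnosis prioritization implies an order at the point of billing. It does not say that the order reaches the analyst. The Aim 1 SAP carries both that sentence and the statement that primary diagnosis is not provided.

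**4. Which primary-field sensitivity analyses are still live?** The protocol plans one for each of four aims (1, 2, 4 and 5). The Aim 1 and Aim 2 SAPs no longer contain it. That leaves 4 − 2 = 2, for Aims 4 and 5, whose SAPs are not among the documents.

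**5. Size.** The effect of a substitute rule would need at least the number of U07.1 inpatient stays, the share with an incidental code and the split by vaccination status. None is stated, so neither size nor direction can be derived.

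**The case against.** The strongest reply is that the protocol is not the last word. Section 8.7 lets a SAP modify it, and each of the three SAPs says: "Separate SAPs will be produced to address the other aims of the protocol". The protocol (15 November 2023) predates the Aim 1 SAP, and its text for Aims 1 and 2 is just as unrevised; those aims were updated only in their SAPs. An Aim 3A SAP may have done the same. This stands as a limit on the point: a reader might infer that Aim 3A has no workable cohort at all, and the documents do not support that. They show only that the one definition available for Aim 3A conflicts with the sponsor's account of the data.

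A second reply is that the absence of the field rests on one clause in one SAP table, and that the prioritization sentence points the other way. That is fair, and it is why the first step is confirmation.

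A third is that the protocol says principal and the SAP says primary. The documents draw no distinction between them for U07.1.

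Three further inferences go too far:

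- The other SAPs did not replace a principal-position rule. For Aims 1 and 2 they narrowed an any-position main definition. Aim 3B never required principal position.
- Not all four primary-field sensitivity analyses still depend on the field. The Aim 1 and Aim 2 SAPs have dropped theirs.
- Childbirth stays are not a serious source of contamination here. Section 8.2.2.3 excludes patients who are pregnant at index, which should remove most of them. Nor does any document propose an any-position fallback for Aim 3A; it is simply the only other inpatient definition in the protocol.

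**Conclusion.** The point holds as a conflict between a stated cohort rule and the sponsor's own description of the data. It affects the whole Aim 3A cohort, adult and pediatric, and the primary-field sensitivity analyses that remain for Aims 4 and 5.

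It rests on two assumptions: that the Aim 1 SAP statement is correct and applies to the Aim 3A extract, and that no Aim 3A SAP has already changed the rule. Neither can be checked from the documents. The consequence for the comparisons of cost, length of stay and ICU admission is unquantified in size and direction, so a reader should not conclude that a particular bias has been shown. The matter should be settled before Aim 3A is programmed, but it does not touch the primary objective's main analysis, which counts U07.1 encounters in any setting and any diagnosis position.

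**What to change.** 1. Confirm with the data supplier whether a principal or primary diagnosis position is delivered for inpatient claims, and reconcile the prioritization sentence (protocol 8.4.2; Aim 1 SAP 5.4.2) with Table 5.2 of the Aim 1 SAP.
2. If it is not delivered, replace the Aim 3A criterion for adults and children, by amendment or in the Aim 3A SAP, with the main hospitalization definition in Table 5.2 of the Aim 1 SAP: a U07.1 inpatient stay without an incidental code, or with COVID-19-only treatment. Keep any-position U07.1 as a sensitivity analysis.
3. In that case also replace the primary-field sensitivity analyses for Aims 4 and 5 with the two in that table. The first applies the frequency test to the incidental code, not to U07.1, and should be carried over in that form. The second takes any U07.1 hospitalization.

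The cost is one query to the supplier and a change of wording. The main definition is already written for Aims 1 and 2 and for the Aim 3B index hospitalizations, so its programming can probably be reused. The frequency-based sensitivity rule appears only in the Aim 1 SAP.

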8.2.1.3.2. Aim 3A Pediatric Inclusion Criteria

- Born in 2006 or later (as age 0-17 years in 2023, owing to the data providing year but not month or day of birth)
- Hospitalized for COVID-19 (an inpatient encounter with ICD-10-CM U07.1 "COVID-19" in the principal diagnosis position)
- At least six months of continuous pharmacy and medical enrollment in HealthVerity prior to index date. Six months was selected to allow for analysis to include children <1 yr due to patient privacy measures in HealthVerity data. A gap of up to 30 days will be allowed.
- 4. Have been a State of California/Louisiana resident for at least six months prior to index date

8.2.1.4. Aim 3B Inclusion Criteria

Aim 3B criteria are different based on the pediatric and adult population analyses as follows:

8.2.1.4.1. Aim 3B Adult Inclusion Criteria

- Born in 2005 or earlier (as age 18 or older in 2023, owing to the data providing year but not month or day of birth).
- At least one year of continuous pharmacy and medical enrollment in HealthVerity prior to index date (i.e. COVID-19 diagnosis). A gap of up to 30 days will be allowed.
- Have been a State of California/Louisiana resident for at least one year prior to index date (i.e. COVID-19 diagnosis)

8.2.1.4.2. Aim 3B Pediatric Inclusion Criteria

- Born in 2006 or later (as age 0-17 years in 2023, owing to the data providing year but not month or day of birth)
- At least six months of pharmacy and medical enrollment in HealthVerity prior to index date.
 Six months was selected to allow for analysis to include children <1 year due to patient privacy measures in HealthVerity data. A gap of up to 30 days will be allowed
- Have been a State of California/Louisiana resident for at least six months prior to index date

